5.3 Screening Procedures

Written informed consent will be provided prior to any study procedures. Documentation of informed consent will be maintained in the subject's research chart and medical

record. Studies or procedures that were performed for clinical indications or as standard of care (not exclusively to determine study eligibility) may be used for baseline values even if the studies were done before informed consent was obtained.

5.3 Placement of Fiducial Markers

Treatment on this protocol requires placement of 3-5 gold fiducials for targeting purposes. The fiducials will be used as surrogates for targeting the daily tumor position during treatment. The fiducials will be placed directly into the tumor, or surrounding normal pancreatic tissue under endoscopic ultrasound or CT guidance. Fiducials may be implanted prior to enrollment as this is an acceptable standard of care procedure for any patient receiving radiotherapy for locally advanced pancreatic cancer. Also, if a patient had an attempted surgical resection that was aborted, fiducials may have been implanted intraoperatively, which is also allowable prior to study enrollment.

Fiducial placement into pancreatic tumors carries a low risk of toxicity [9,10]. In one report of 50 patients who had fiducials implanted into the pancreas through endoscopy only one patient (2%) had minor bleeding without a significant drop in hemoglobin, and this event did not require hospitalization [10]. In another report of 61 patients who had fiducials implanted percutaneously under CT guidance only two patients (3.3%) had minor bleeding episodes [9].

6.0 RADIATION THERAPY

6.1 Pre-SBRT tests and procedures

6.1.0 Pre-SBRT tests

- Medical history and clinical examination.
- CBC, Chemistry Panel, CA19-9.
- Gold fiducial seed placement percutaneously, intraoperatively, or under endoscopic ultrasound guidance, which may be performed prior to enrollment.
- Signed informed consent document.

6.1 External Beam Radiation Therapy

6.1.0 Patient setup and simulation

6.1.0.1 Position

CT simulation will be done in the supine position with patient in an Alpha Cradle, or Vac-Lok for immobilization.

6.1.0.2 Imaging

All subjects will undergo a 3-dimensional (3D) CT scan with intravenous contrast, and slice thickness ≤ 2.5 mm. This 3D scan should preferably be done during an expiratory breath hold phase. Following the 3D CT, a four-dimensional (4D) CT scan with respiratory gating will be done to account for tumor motion. CT scans should include T4/T5 to L5/S1.

6.1.0.3 Contrast

Intravenous contrast is used during the CT simulation scan. If a patient cannot

receive IV contrast then an MRI can be done and fused to the treatment planning CT scan. Oral contrast will consist of a cup of water that the patient will drink 30 minutes before the simulation.

6.1.1 Treatment planning

6.1.1.1 Planning CT scan

The treatment planning CT scan will be defined as the CT from simulation that most clearly shows the tumor and adjacent normal tissue, and can be any of the following:

- 1) Expiratory phase of the 4D CT scan (50%);
- 2) Expiratory 3D CT simulation scan
- 3) Average of select sequences from the 4D CT scan around expiration including 30%, 40%, 50% (end expiration), 60%, and 70%.

6.1.1.2 CT fusion

When available, a recent diagnostic pancreas protocol CT, PET/CT, or abdominal MRI should be fused with the planning CT scan, using fiducial-to-fiducial fusion if possible.

6.1.1.3 Tumor target delineation

The pancreas gross tumor volume (GTV) will be identified on the treatment planning CT scan. The internal target volume (ITV) will be defined by the attending radiation oncologist using the 4D CT scan to account for respiratory motion. The final planning target volume (PTV) will consist of a 2-3 mm expansion around the ITV. The PTV can be trimmed off of the duodenum or stomach at the treating physician's discretion. Elective nodal regions will not be irradiated.

6.1.1.4 Treatment planning

Treatment will consist of 6 MV or 15 MV photons directed at the PTV using 6-12 fields or a modulated arc technique. Intensity modulated radiation therapy (IMRT) techniques such as fixed-field IMRT, or volume modulated arc therapy (VMAT) can be used to reduce dose to surrounding normal tissues. The dose should be prescribed as follows:

- 1) 90-95% of the PTV (preferably 95%) should receive 100% of the prescription dose
- 2) No more than 1 cm³ of the PTV can receive >120% of the prescription dose

6.1.1.5 Normal tissue constraints

Normal tissue dose should be minimized. Specific organ constraints are as follows.

- 1) **Duodenum:** no more than 1 cm³ of duodenum may exceed the prescription dose.
- 2) **Stomach:** no more than 1 cm³ of the stomach may exceed the prescription dose.
- 3) **Small bowel (excluding duodenum):** no more than 1 cm³ of small bowel may exceed the prescription dose.
- 4) **Large bowel:** no more than 1 cm³ of large bowel may exceed the prescription dose.
- 5) **Liver:** 700 cm³ of normal liver should receive less than a mean dose of 15

Gy.

- 6) **Kidneys (combined)**: combined volume should have 75% <12 Gy.
- 7) **Spinal cord**: no more than 1 cm³ should exceed 8 Gy.
- 8) *If the above tumor and normal tissue constraints cannot be made then the prescription dose to the PTV can be reduced such that 100% of the GTV will receive the prescription dose. If this constraint cannot be met, then the patient should be removed from the protocol.*

6.1.1.6 Heterogeneity corrections

Heterogeneity corrections should be applied.

6.1.2 Treatment delivery

Patients will receive 5 fractions over a five day period. Treatment should start preferably on Monday, and extend through the following Friday, though it may extend over 2 weeks if scheduling issues arise.

Patient position will be verified daily before each treatment with the following

- 1) Orthogonal kV/kV imaging focusing on bone anatomic alignment.
- 2) Daily cone-beam CT before and after each treatment will be conducted to verify anatomic location and stability. 4DCBCT should be used if available.
- 3) Fluoroscopy will be used to confirm that the tumor fiducials fall within the respiratory gating window (aperture). The gating window or patient position should be adjusted to ensure precise positioning.

6.2 Radiation Adverse Events

Risks and side effects related to radiation include:

Likely (more than 10%)

- Tiredness
- Nausea
- Damage to the duodenum, stomach, or intestine including ulceration, bleeding, or perforation which may require surgery or hospitalization.

Less Likely (3-9%)

- Redness and skin irritation in the treatment area
- Vomiting or dehydration

Rare, but serious (less than 2%)

- Development of an abnormal pathway or connection between organs (fistulae) including the duodenum, stomach, and blood vessels in the abdomen such as the aorta which may require hospitalization or surgery
- Damage to the liver causing liver failure
- Damage to the kidney causing kidney failure
- Damage to the spinal cord resulting in paralysis

7.0 DRUG THERAPY

7.1 Chemotherapy

Chemotherapy is not specified per protocol. Prior to enrollment, or after completion of SBRT patients may receive standard chemotherapy, or other investigational agents at the discretion of their treating oncologist. Patients may not receive chemotherapy during or within 7 days (before or after) pancreas SBRT.

8.0 OTHER THERAPY

8.1 Permitted Supportive Therapy/Procedures:

8.1.1 Antiemetic Agents

Standard antiemetic agents are allowed at the discretion of the treating physician.

8.1.2 Antidiarrheal Agents

Standard antidiarrheal agents are allowed at the discretion of the treating physician.

8.1.3 Analgesics

Standard analgesics, both narcotic and non-narcotics, are allowed at the discretion of the treating physician.

8.1.4 Nutritional supplementation

Nutritional supplementation, both by mouth and by enteric feeding tube, is allowed at the discretion of the treating physician.

9.0 PATHOLOGY

All patients will have pathologically confirmed pancreatic adenocarcinoma. Central review of pathology is not required.

10.0 PATIENT ASSESSMENTS

10.1 Study Parameters

Table 2

Study Procedures	Pre-Treatment	Week 1	Post-Treatment ^b
Informed Consent	X		
History and Physical	X		
Physical Exam with Vital Signs	X	X	1,3,6,9, 12 months, and every 6 months thereafter
CBC with differential, and comprehensive metabolic panel ^a	X		

CA 19-9	X		3, 6, 12, and every 6 months thereafter, or until disease progression
CT Abdomen, and Pelvis	X		3, 6, 12, and every 6 months thereafter, or until disease progression
Treatment: SBRT		D1-5	
Clinical evaluation for Toxicity	X	X	1,3,6,9, 12 months, and every 6 months thereafter
EORTC QLQ C-30/PAN26 questionnaire ^c	X		1,3,6,9, 12 months, and every 6 months thereafter

^a Electrolytes including Creatinine, Bilirubin, SGOT, and SGPT

^b Visit should occur at timepoints above +/- 28 days

^c See appendix for details on questionnaire

10.2 Adverse Events (AEs)

Adverse event information will be documented on appropriate case report forms (CRF) which will include timing, severity and perceived causation of the events and followed until they either stabilize or resolve.

This study will utilize the Common Terminology Criteria for adverse events (CTCAE) of the National Cancer Institute for reporting of adverse events within 90 days after completion of radiation therapy. A copy of the current version of the CTCAE version 4.0 can be downloaded from the CTEP home page (<http://ctep.cancer.gov/reporting/ctc.html>). Adverse events after 90 days after completion of radiation therapy will be scored with the RTOG/EORTC Late Radiation Morbidity Scoring Schema. A copy of the current version of the RTOG/EORTC scale is available on the RTOG home page (<http://www.rtoq.org/ResearchAssociates/AdverseEventReporting/RTOGEORTCLateRadiationMorbidityScoringSchema.aspx>).

Definition of an AE: any untoward medical occurrence in a patient receiving study treatment and which does not necessarily have a causal relationship with this treatment. An AE can therefore be any unfavorable and unintended sign (including a clinically significant abnormal laboratory finding), symptom, or disease temporally associated with the use of an experimental intervention, whether or not related to the intervention.

Serious Adverse Events (SAEs)

A serious adverse event is defined in regulatory terminology as any untoward medical occurrence that:

- **Results in death.**
If death results from (progression of) the disease, the disease should be reported as event (SAE) itself.
- **Is life-threatening.**
(the patient was at risk of death at the time of the event; it does not refer to an event that hypothetically might have caused death if it were more severe).
- **Requires in-patient hospitalization or prolongation of existing hospitalization for ≥ 24 hours.**
- **Results in persistent or significant disability or incapacity.**

- **Is a congenital anomaly/birth defect**
- **Is an important medical event**

Any event that does not meet the above criteria, but that in the judgment of the investigator jeopardizes the patient, may be considered for reporting as a serious adverse event. The event may require medical or surgical intervention to prevent one of the outcomes listed in the definition of "Serious Adverse Event".

10.3 Steps to Determine If Expedited Reporting for an Adverse Event is Indicated

Step 1: Identify the type of adverse event using the CTCAE v4. The CTCAE v4 provides descriptive terminology and a grading scale for each adverse event listed. A copy of the CTCAE v4 can be downloaded from the CTEP home page (<http://ctep.cancer.gov/reporting/ctc.html>). Additionally, if assistance is needed, the NCI has an Index to the CTCAE v4 that provides help for classifying and locating terms.

Step 2: Grade the adverse event using the NCI CTCAE v4.

Step 3: Determine whether the adverse event is related to the protocol therapy
Attribution categories are as follows:
Unrelated, Unlikely Related, Possibly Related, Probably Related, and Definitely Related.

Note: This includes all events that occur within 30 days of the last dose of protocol treatment. Any event that occurs more than 30 days after the last dose of treatment and is attributed (possibly, probably, or definitely) to the agent(s) must also be reported according to the instructions above.

Step 4: Determine the prior experience of the adverse event. Expected events are those that have been previously identified as resulting from administration of the agent. An adverse event is considered unexpected, for expedited reporting purposes only, when either the type of event or the severity of the event is not listed in:

- the current known adverse events listed in the Agent Information Section of this protocol;
- the investigator's brochure or the drug package insert

Step 5: Review Section 10.6 to determine if:

- there are any protocol-specific requirements for expedited reporting of specific adverse events that require special monitoring; and/or
- there are any protocol-specific exceptions to the reporting requirements.

10.4 Reporting Requirements for Adverse Events

Expedited Reporting

- The Principal Investigator must be notified within 24 hours of learning of any serious adverse events, regardless of attribution, occurring during the study.
- The UCSD Human Research Protections Program (HRPP) and the Moores Cancer Center Data and Safety Monitoring Board (DSMB) must be notified

within 10 business days of “any unanticipated problems involving risk to subjects or others” (UPR).

The following events meet the definition of UPR:

1. Any serious event (injuries, side effects, deaths or other problems), which in the opinion of the Principal Investigator was unanticipated, involved risk to subjects or others, and was possibly related to the research procedures.
2. Any serious accidental or unintentional change to the IRB-approved protocol that alters the level of risk.
3. Any deviation from the protocol taken without prior IRB review to eliminate apparent immediate hazard to a research subject.
4. Any new information (e.g., publication, safety monitoring report, updated sponsor safety report), interim result or other finding that indicates an unexpected change to the risk/benefit ratio for the research.
5. Any breach in confidentiality that may involve risk to the subject or others.
6. Any complaint of a subject that indicates an unanticipated risk or that cannot be resolved by the Principal Investigator.

Routine Reporting

- The UCSD HRPP will be notified of any adverse events that are not unanticipated problems involving risk to subjects or others (non-UPRs) at the time of the annual Continuing Review.
- The FDA will be notified of all other adverse events that do not meet the criteria for expedited reporting at the time of the IND Annual Report.

10.5 Criteria for Removal from Protocol Therapy

- a) Adverse Events requiring removal from study.
- b) Non-compliance that in the opinion of the investigator does not allow for ongoing participation.
- c) Physician determines it is in the subject's best interest.

10.6 Criteria for Removal from Study

- a) Loss to follow-up.
- b) Withdrawal of consent for any further data submission.

11.0 DATA COLLECTION

11.1 Data and Safety Monitoring Plan

In addition to adverse event monitoring and clinical oversight by the principal investigator and co-investigators, quality assurance of the study will be performed by the clinical trials office internal monitor. Monitoring intervals will be dependent upon the number of patients enrolled.

This study will also use the UCSD Moores Cancer Center Data Safety and Monitoring Board to provide oversight in the event that this treatment approach leads to unforeseen toxicities. The DSMB will review data from this study semi-annually.

Data from this study will be reported semi-annually and will include:

- 1) the protocol title, IRB protocol number, and the activation date of the study.
- 2) the number of patients enrolled to date
- 3) the date of first and most recent patient enrollment
- 4) a summary of all adverse events regardless of grade and attribution
- 5) a response evaluation for evaluable patients
- 6) a summary of any recent literature that may affect the ethics of the study.

11.2 Confidentiality Procedures

Recruitment procedures will involve the review of patient records by designated study personnel (e.g., investigators and/or study coordinators) in order to identify potentially eligible patients. Since Protected Health Information (PHI) will be accessed via the hospital's medical record database and scheduling system (e.g., CPRS) prior to contacting the potential subject about the research study, we are requesting a partial waiver of HIPAA authorization for access to PHI for purposes of prescreening only. Standard HIPAA authorization to collect research data from the subject's medical record will be obtained at the time of informed consent.

Protected health information (PHI) will be maintained in the subjects' medical charts and thus confidentiality is protected via routine procedures. Data specific to this study will be kept in an electronic database to which only the principal investigator and involved study personnel will have access. The database will be de-identified by removing subjects' names and assigning a unique identifier to each subject. The database will be maintained on a protected disk drive in the radiation oncology department.

12.0 STATISTICAL CONSIDERATIONS

12.1 Statistical Analysis

12.1.1 Primary Endpoint: The purpose of this study is to determine the maximum tolerated dose (MTD) of five fraction SBRT in pancreatic cancer. The MTD will be defined from dose limiting toxicity, which will represent grade ≥ 3 gastrointestinal (GI) toxicity. GI toxicity from SBRT can occur anywhere from 6 weeks to 1 year after SBRT, with the median time to a toxic event being 6 months [6]. Because of the long "window" for toxicity a classic phase I 3+3 dose-escalation trial design would require a substantial amount of time between enrolled subjects to observe for toxic events. Therefore, to improve efficiency this study will use a time to event continual reassessment method (TITE-CRM) trial design [11], described in more detail below.

12.1.2 Secondary Endpoints

12.1.2.1 Local control. The cumulative incidence of local failure will be determined for all patients treating distant progression or death as a competing

risk. Local progression will be defined as a $\geq 20\%$ increase in size on CT compared with CT prior to SBRT.

12.1.2.2 Distant metastatic progression rate. The cumulative incidence of distant metastatic failure will be determined for all patients treating death as a competing risk. In patients initially presenting with locally advanced disease, distant disease progression will be defined as the appearance of new metastatic lesions. In patients presenting with metastatic disease, distant progression will be defined as a $\geq 20\%$ increase in size on CT of the previously noted metastatic lesions.

12.1.2.3 Overall survival. Overall survival will be measured from the date of diagnosis through death of any cause. Survival will also be reported from the date of SBRT for comparisons to other trials in the literature. Finally, survival will be stratified by those with locally advanced disease, and those with metastatic disease on presentation.

12.1.2.4 Dose response. An exploratory analysis evaluating for a correlation between radiation dose response and local control will be done with a competing risk analysis, dividing patients into two groups stratified by the median dose..

12.1.2.5 Longitudinal quality of life. We will track longitudinal quality of life using the European Organization for Research and Treatment in Cancer (EORTC) quality of life core cancer questionnaire with the pancreatic cancer module (EORTC QLQ C-30/ PAN26) (see appendix). The questionnaire will be given prior to treatment, and periodically during follow-up visits after treatment has concluded. Trends will be assessed with a linear mixed effects model.

12.1.2.6 Correlation between quality of life and disease progression. Disease progression is a commonly used surrogate endpoint in clinical trial with pancreas cancer, however its relationship with quality of life has not clearly been demonstrated. Therefore, we will assess for correlation between quality of life and local or distant disease progression.

12.1.2.7 Dose-volume relationship with duodenal/gastric toxicity. We will plan to use logistic regression models to determine the relationship between grade ≥ 3 duodenal or gastric toxicity and dose to these structures. The dose to the duodenum will be extracted from our treatment planning system.

12.1.2.8 Ability to receive additional chemotherapy. We will determine the fraction of patients who are able to receive additional chemotherapy among those whose initial intent was to do so. After consultation with an oncologist, but prior to treatment, we will record whether patients wish to receive additional chemotherapy after the course of chemo-radiotherapy delivered with this study. Possible responses include: yes, no, or undecided. We will then record who receives subsequent chemotherapy after completing treatment in our protocol.

12.1.2.9 Surrogate target discovery. We will determine the natural anatomical surrogates that best correlate with the motion of the fiducial markers. Potential surrogates include the superior mesenteric vessels, aorta, portal vein, and soft-tissue border of the pancreas. This information will help treat pancreas cancer

patients using image guidance technologies who could not have the markers placed.

12.1.2.10 Adaptive RT strategies. We will conduct a study to determine the best adaptive RT strategies that maximize the therapeutic ratio based on analyzing the information contained in the daily imaging studies to be performed on the patients.

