1.0 INTRODUCTION

1.1 Pancreatic Cancer

Pancreatic cancer is the 10th most common cause of cancer, and the 4th most common cause of cancer-related death in the United States, with an annual incidence of 45,220 new diagnoses per year [1]. The only curative treatment for pancreatic cancer is surgery, yet approximately 75% of patients present with unresectable or metastatic disease. Of those patients with surgically resectable disease, the 5-year survival is around 20%. Among those with unresectable disease distant metastatic spread remains the primary problem, though up to 1/3 of patients will die from local tumor progression [2]. Additionally, local tumor progression leads to pain, gastrointestinal obstruction, or bleeding, all of which substantially decrease a patient's quality of life. Thus, local tumor control remains a crucial part of treatment for patients with pancreatic cancer who are not candidates for curative therapy.

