2.2 Secondary Aims

- 2.2.1 To estimate the rate of local tumor progression after SBRT.
- 2.2.2 To estimate the rate of distant disease progression after SBRT.
- 2.2.3 To measure overall survival after SBRT.
- 2.2.4 To estimate a dose-response between radiation dose and local control.
- 2.2.5 To measure longitudinal quality of life before and after SBRT.

- 2.2.6 To determine the correlation between quality of life, and disease progression after SBRT.
- 2.2.7 To determine if any dose-volume parameters predict grade ≥ 3 duodenal toxicity.
- 2.2.8 To determine if patients are able to receive additional chemotherapy after SBRT.
- 2.2.9 To identify natural anatomical surrogates that best correlate with the motion of the fiducial markers.
- 2.2.10 To determine if adaptive RT would be beneficial.

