3.1 Inclusion Criteria

- 3.1.1 Diagnosis: Histologically-proven invasive adenocarcinoma of the pancreas.
- 3.1.2 Disease Status: Medically unresectable (stage I-II), or locally advanced (stage III). Patients with distant metastases (stage IV) must have stable disease or improved disease (partial response, or complete response) per Response Evaluation Criteria In Solid Tumors (RECIST) criteria as determined on serial imaging following a course of chemotherapy.
- 3.1.3 Tumor Location: Primary tumor may be located anywhere in the pancreas.
- 3.1.4 Treatment eligibility: The patient must be able to have fiducial markers implanted into the pancreatic tumor, and receive radiation regimen as specified in the protocol.
- 3.1.5 Performance Level: Karnofsky Performance Status ≥ 60 (see Appendix II)
- 3.1.6 Adequate Renal Function Defined As:
 - Serum creatinine $\leq 1.5 \times$ upper limit of normal
- 3.1.7 Age: Patients must be 18 years of age or older.
- 3.1.8 Informed Consent: All subjects must sign a written informed consent.

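### Section 12.1.2.1 counts distant progression as a competing event for local failure, so it estimates local failure as first event, which can only be at or below the local progression rate in aim 2.2.1

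*Combined protocol and SAP*

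**What the plan says.** Aim 2.2.1 reads "To estimate the rate of local tumor progression after SBRT". It is not restricted to patients whose first event is local.

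Section 12.1.2.1 serves that aim with a cumulative incidence of local failure, "determined for all patients treating distant progression or death as a competing" risk. Local progression is a size criterion: at least a 20% "increase in size on CT compared with CT prior to SBRT".

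Section 12.1.2.2 handles the companion endpoint differently: "The cumulative incidence of distant metastatic failure will be determined for all patients treating death as a competing risk". Local progression does not compete there, and no reason is given for the difference.

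Section 12.1.2.4 plans an exploratory dose-response analysis of local control by competing-risk methods. It does not say which events compete.

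Table 2 in section 10.1 schedules abdominal and pelvic CT at "3, 6, 12, and every 6 months thereafter, or until disease progression", without saying whether local or distant progression is meant.

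**The concern.** A competing event should make the event of interest impossible. A living patient with a new metastasis still has a pancreatic tumor, and it can still grow by 20%. Under 12.1.2.1 such a patient leaves the local-failure risk set at distant progression, and any later local failure goes uncounted.

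Section 1.1 says that "distant metastatic spread remains the primary problem, though up to 1/3 of patients will die from local tumor progression". Removal through distant progression is therefore unlikely to be rare, and local failure after metastasis is part of the harm that SBRT is meant to prevent.

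At stake is what the reported number means. The first-event incidence falls when distant spread is fast, whatever SBRT does to the primary tumor. Presented as the local progression rate, it would make local control look better than it is. If 12.1.2.4 adopts the same events, a chance difference in distant progression between the two dose groups could look like a dose effect on local control.

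**Working it through.** The plan gives no expected local failure rate or precision for aim 2.2.1, so there is no planned figure to reproduce.

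**Direction.** Let L, D and X be the times to local failure, distant progression and death. The plan counts patients with L < min(D, X). With death as the only competing event, one counts those with L < X. The first group is a subset of the second, so the planned incidence cannot be larger. It is smaller as soon as one patient has D < L < X. This needs no assumed figure.

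**Size: inputs from the documents**
- Median survival 8.25 months (12.2.1).
- Low local hazard, from 84% one-year freedom from local progression (1.4): λL = −ln(0.84)/12 = 0.0145 per month.
- High local hazard, from local control of about 50% (1.3), read as a 12-month value, which is an assumption: λL = ln(2)/12 = 0.0578 per month.

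**Size: assumptions not in the documents**
- Median time to distant progression of 4, 6, 9 or 12 months, with λD = ln(2)/median.
- Death hazard μ before distant progression and kμ after it, with k = 1 or 3. μ is solved so that median survival is 8.25 months.
- Constant hazards, local hazard unchanged by distant progression, local failure not affecting death, and continuous detection.

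**Formulas, 12-month cumulative incidence**
- As planned: λL/(λL+μ+λD) × [1 − exp(−12(λL+μ+λD))].
- Death only: the integral from 0 to 12 of λL·exp(−λL·t)·S(t) dt, where S(t) = exp(−at) + λD[exp(−bt) − exp(−at)]/(a−b), a = μ+λD, b = kμ.

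**Worked example** (median 6 months, k = 3, so λD = 0.1155 and μ = 0.0523)
- Low hazard: the sum of hazards is 0.0145+0.0523+0.1155 = 0.1823. As planned, 0.01453/0.1823 × (1 − exp(−2.188)) = 0.0797 × 0.888 = 7.1%. Death only, 10.4%. A simulation of 2,000,000 patients gave 7.07% and 10.44%.
- High hazard: the sum is 0.2256. As planned, 0.0578/0.2256 × (1 − exp(−2.707)) = 23.9%. Death only, 34.1%.

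**All scenarios** (death only / as planned / ratio)

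| Median to distant progression, months | k | Low local hazard | High local hazard |
|---|---|---|---|
| 4 | 1 | 10.2% / 5.1% / 0.50 | 33.3% / 17.9% / 0.54 |
| 4 | 3 | 10.5% / 5.8% / 0.56 | 34.2% / 20.1% / 0.59 |
| 6 | 1 | 10.2% / 6.3% / 0.61 | 33.3% / 21.4% / 0.64 |
| 6 | 3 | 10.4% / 7.1% / 0.68 | 34.1% / 23.9% / 0.70 |
| 9 | 1 | 10.2% / 7.3% / 0.71 | 33.3% / 24.5% / 0.74 |
| 9 | 3 | 10.4% / 8.1% / 0.78 | 33.9% / 26.9% / 0.79 |
| 12 | 1 | 10.2% / 7.9% / 0.77 | 33.3% / 26.3% / 0.79 |
| 12 | 3 | 10.4% / 8.6% / 0.83 | 33.8% / 28.5% / 0.84 |

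The ratios run from 0.50 to 0.84, a relative loss of 16% to 50%. In 30 patients the low-hazard example is 30 × (0.104 − 0.071) = 1.0 patient.

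**Scan intervals.** CT is at 3, 6 and 12 months in the first year, so local and distant progression will often appear on the same scan. The plan has no rule for such ties. Assigning events to those scans, with medians of 4 to 8 months and a death hazard before distant progression 0.3 times that after, the relative loss is about 9–23% if ties count as local and 29–54% if they count as distant.

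**The case against.** Local failure before distant progression or death is a valid cumulative incidence, and 12.1.2.1 states its competing events openly. The estimator is therefore sound for its own target; the mismatch is with aim 2.2.1. This stands, and relabelling is an acceptable remedy.

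Table 2 suggests a practical reason for the rule, though the plan does not give it: if CT stops at distant progression, later local failures are not seen. This also stands. Changing only the competing event would then keep unimaged patients in the risk set as if locally controlled, and failure would again be understated. Editing one sentence in 12.1.2.1 is not enough.

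Three stronger inferences are tempting but not supported:
- *Enrolling stage IV patients contradicts the rule.* Section 3.1 says "Patients with distant metastases (stage IV) must have stable disease or improved disease". The competing event is distant progression, not the presence of metastases, and 12.1.2.2 defines progression for these patients too. They leave the risk set when it occurs.
- *The correction makes the result comparable with the 84% in section 1.4.* Taken as a net risk, 84% freedom implies 16% failure, while the death-only incidence is about 10%. The documents do not say how the 84% was estimated.
- *The dose-response analysis is affected for certain.* Section 12.1.2.4 names no competing events, so this is inference, and that analysis is labelled exploratory.

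**Conclusion.** The point holds as a mismatch between aim 2.2.1 and the analysis in 12.1.2.1. The planned figure is local failure as first event; it cannot exceed the local progression rate and will generally lie below it. That direction rests on no assumed rate.

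The magnitude is only illustrative. The 16–50% relative loss depends on the assumed timing of distant progression, the death hazards, independence of local failure from distant spread, and continuous detection; tie handling at scheduled scans shifts it further. In absolute terms the low-hazard example is about one patient in 30, where the sampling error is much larger: the exact 95% interval for 3 of 30 is 2% to 27%.

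A reader might infer that the trial's main conclusion is at risk. It is not: the MTD, escalation, stopping rules and sample size do not use this endpoint, and section 1.4 leaves efficacy to a later phase II trial. The point should be fixed, but it is not critical.

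**What to change.** 1. In 12.1.2.1, make death without prior local failure the only competing event, and keep patients at risk after distant progression.
2. In 12.1.2.4, state that the same event definition applies.
3. Reconcile this with Table 2. Either clarify that, for this endpoint, CT runs until local progression, or use CTs obtained in routine care after distant progression and censor at the last evaluable CT. In the second case, state the assumption that this censoring is independent of local failure.
4. Report local failure as first site of progression separately, with a rule for local and distant progression found on the same scan.
5. If local status will not be imaged after distant progression, keep the planned analysis, label it *local failure as first event*, and do not present it as the local progression rate.

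The cost is a short edit to two sections and a clarification in Table 2. Local measurement continues after distant progression, which may mean further CTs or retrieval of routine ones, and the reported local failure rate becomes somewhat less favourable. Best settled early, because local failures that were not imaged cannot be recovered later.
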